- Subjects that are 3 weeks to 6 months post liver transplant will be screened for the study. After eligibility is established and informed consent document has been signed by the patient or representative, subjects will be randomized to spironolactone 25 mg daily, or no treatment. Non-English only speaking subjects will be consented with an interpreter. A total of 36 patients will be randomized (50/50), 18 to treatment and 18 to standard of care. Subjects that do not wish to enroll or do not meet the criteria for the main study may choose to participate in the sub-study if they are not allergic to iodine and if their GFR is greater than 30 ml/min. 36 subjects may be enrolled in the sub-study to compare the currently used method of evaluating kidney function based on serum creatinine to other measures of creatinine clearance and kidney filtration rate (iothalamate GFR, 24 hour urine for creatinine clearance and protein, serum cystatin C, basic metabolic package and serum albumin).

Inclusion Criteria

- Liver transplant within 3 weeks to 6 months of study enrollment.
- Age 18-75 years old
- Proteinuria less than 3 g/24 hours
- Creatinine Clearance greater than 30 ml/min
- Negative pregnancy test for women of child bearing potential

Exclusion Criteria

- Patients on angiotensin converting inhibitors or angiotensin receptor blockers, digoxin, other drugs associated with hyperkalemia (dapsone can be substituted for sulfamethoxazole if needed at the discretion of the investigator)
- Potassium greater than 5.2 meq/L on screening labs, one occasion in a non-hemolyzed specimen,
- Prior intolerance to spironolactone
- Factors, that in the opinion of the investigator, would interfere with subject's compliance with the study
- Retransplantation
- Combined organ transplant-i.e. liver kidney, liver-heart
- Subjects who are anticipated to be placed on sirolimus or everolimus due to underlying condition (i.e. patients with HCC outside Milan criteria or with vascular invasion). Other

renal sparing protocols are allowed in including initial treatment with simulect, CNI reduction with mycophenolate mofetil

- Allergic to iodine

Patients will be monitored by SOC transplant protocol for up to 2 years.

For those subjects on treatment, if potassium stays less than 5.2 meq/L after 1 month on treatment, spironolactone may be increased to 50 mg daily at the discretion of the investigator.

4. Statistical analysis:

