Mean GFR will be compared using unpaired Students' T test between groups and paired Students' t test within groups. If creatinine clearance is not normally distributed a nonparametric test will be used (Wilcoxon rank sum test) to compare creatinine clearance between groups. Sample size: 16 subjects in each group will be needed to detect a 10 ml difference in creatinine clearance with a power of 0.5 at $p \leq 0.05$.

5. Outcomes:

Primary outcome

- Change in creatinine clearance from screening to 1 year post randomization based on iothalamate GFR (glomerular filtration rate).
- Renal function tests will be compared to the iothalamate GFR to determine which best approximates the Glofil results.

Secondary outcomes

- Patient survival
- Graft Survival
- 6 month and 18 month creatinine clearance
- Dialysis
- Hyperkalemia ($>5.5 \text{ mEq/L}$)
- Proteinuria as defined by $> 3 \text{ g/24h}$

- Discontinuation for adverse events
- Conversion to renal sparing immunosuppressive regimen
- Number of subjects requiring sodium bicarbonate (NaHCO₃)
- Calculation of CKD-EPI, CKD-EPI Cystatin, CKD-EPI-Cystatin-Creatinine, MDRD-4, MDRD-6 and 24 hour urine creatinine clearance at screening and 6, 12, 18, and 24 months. Comparison of the currently used method of evaluating kidney function based on serum creatinine to other measures of creatinine clearance and kidney filtration rate (CKD-EPI, CKD-EPI Cystatin, CKD-EPI-Cystatin-Creatinine, MDRD-4, MDRD-6, 24 hour urine creatinine clearance and iothalamate GFR).

6. Study Calendar of Events

	Screening	Randomization	Day 7	Wk 2	Wk 3	Wk 4	MONTHLY until month 24	MONTHS 6,12,18,24
	45 days from screening	±2 days	±2 days	±2 days	±2 days	±5 days	±2 weeks	
History and physical	X							
Vitals signs (if recorded as part of the standard of care visit)	X	X	X	X	X	X	X	
ECG	X							
CHEM-7	X	X	X	X	X	X*		
Albumin level (standard of care lab within 30 days)	X						X	
24 HR creatinine clearance and 24 hour urine protein							X	
Cystatin C		X						X

		[name]					
		ONLY 12, 24 MONTHS					
Iothalimate GFR **		X					
Adverse events		X					
BLOOD FOR DNA ANALYSIS (Preferably collected at randomization, but may be collected at any post-randomization visit)		X					

*BMP weekly for 2 weeks if dose change in spironolactone or addition of NaHCO₃

**Depending in the budget a subset of subjects may undergo iothalimate scans at baseline and 1 year

7. Safety and Monitoring Plan

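### The only proteinuria outcome is a yes/no count above 3 g/24 h in subjects who must enter below it; a baseline-adjusted analysis of log 24-hour protein should be added

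*Combined protocol and SAP*

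**What the plan says.** - Section 5, secondary outcomes: "Proteinuria as defined by" more than 3 g in 24 hours. No other proteinuria outcome is listed.
- Section 3, inclusion criteria: "Proteinuria less than 3 g/24 hours".
- Section 6, calendar: a row for "24 HR creatinine clearance and 24 hour urine protein", so the quantity is measured on study. The table is broken in the text available to me, and the visits cannot be read with certainty.
- Section 3, allocation: "A total of 36 patients will be randomized (50/50), 18 to treatment and 18 to standard of care".
- Section 4: "Mean GFR will be compared using unpaired Students' T test between groups and paired Students' t test within groups", with a Wilcoxon test for creatinine clearance if it is not normally distributed. No method is given for proteinuria, as a count or as a measurement.
- No section gives an expected rate of crossing 3 g, a proteinuria distribution or a proteinuria effect size.

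**The concern.** The threshold for the outcome is the same as the ceiling for entry. A subject who goes from 0.3 to 2.8 g and one who goes from 2.8 to 0.3 g are both recorded as no event, exactly like a subject who never changed. A benefit of spironolactone could show only as fewer new crossings than in the control arm, and only if enough controls cross.

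Specific Aim (a) asks whether spironolactone reduces calcineurin-inhibitor nephrotoxicity, and the primary comparison is sized for power of only 0.5. Supporting kidney measures therefore carry some weight. Most of the others in section 5 concern filtration, so proteinuria adds a different kind of evidence. A count that would probably show no difference even if protein excretion halved makes poor use of a 24-hour collection that is already scheduled.

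**Working it through.** **1. The plan's own figure.** The only sample-size statement concerns creatinine clearance: "16 subjects in each group will be needed to detect a 10 ml difference in creatinine clearance with a power of 0.5 at" the 0.05 level. No SD is given, so it can only be solved backwards. With SD = Δ·√(n/2)/(z_α + z_power) and z for power 0.5 equal to 0, a two-sided test gives 10 × √8 / 1.96 = 14.4 ml (17.2 ml if one-sided). There is no corresponding figure for proteinuria to reproduce.

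**2. Events needed.** Fisher exact test, two-sided, 18 v 18. This needs no assumption about the protein distribution.

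| Control v spironolactone events | p |
|---|---|
| 4 v 0 | 0.104 |
| 5 v 0 | 0.045 |
| 6 v 1 | 0.088 |
| 7 v 1 | 0.041 |

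At least 5/18 = 28% of controls must develop more than 3 g/24 h, with none on spironolactone. With 16 per arm the minimum is still 5 v 0 (p = 0.043).

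**3. Information lost by the cut.** Take a shift between arms on a scale where protein is normal (such as the log), and let p be the share of subjects above the cut. The efficiency of the cut relative to the continuous comparison is φ(z_p)²/[p(1 − p)]. At p = 0.02, z = 2.054 and φ = 0.0484, so the efficiency is 0.0484²/(0.02 × 0.98) = 0.12, a loss of 88%. The rates below are assumed. The last column is the Fisher power for a shift of 0.96 SD, which a t-test at 18 per arm detects with 80% power; for that column, p is the control-arm rate.

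| Assumed share above 3 g | Information lost | Power of the count |
|---|---|---|
| 1% | 93% | about 0 |
| 2% | 88% | about 0 |
| 5% | 78% | 0.1% |
| 10% | 66% | 2.3% |
| 20% | 51% | 16.6% |
| 30% | 42% | 30.4% |
| 50% | 36% | 44.7% |

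If the rate is 1%, 2% or 5% in both arms, the chance of no event at all among 36 subjects is (1 − p)^36 = 70%, 48% or 16%.

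**4. Power for a stated change in protein.** Assume log-normal protein with median 0.5 g. A halving is ln 2 = 0.693 on the log scale. Adjusting for baseline with correlation r reduces the SD to SD·√(1 − r²). Power is for a two-sided t-test at 0.05 with 18 per arm.

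- Log-SD 0.9, r = 0.6: residual SD = 0.9 × 0.8 = 0.72; 0.693/0.72 = 0.96 SD; power about 0.80.
- Log-SD 1.2, r = 0.3: residual SD = 1.2 × √0.91 = 1.145; 0.693/1.145 = 0.61 SD; power about 0.42.
- No baseline adjustment, log-SD 0.9: 0.693/0.9 = 0.77 SD; power about 0.61.

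Simulation with entry capped below 3 g agrees: about 0.79 and 0.42 for the two adjusted settings and about 0.63 for the unadjusted one. In the first setting about 0.4 crossings are expected in the whole trial. The power of the count is below 0.01 in both adjusted settings.

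Smaller effects, with log-SD 0.9 and r = 0.6: adjusted power is about 0.5 for a 40% reduction and about 0.2 for a 25% reduction.

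**The case against.** **The count is coherent.** It stands in a list with dialysis, hyperkalemia and discontinuation for adverse events. Read as a tally of new heavy proteinuria, entry below the threshold is what makes it valid. This stands: the definition is not an error, and the count should be kept.

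**No test is planned for it.** A reader might infer that the trial is bound to report no difference whatever spironolactone does. The plan names no test for proteinuria, and a rare-event count can simply be described. What remains is that the count carries little comparative information, however it is reported.

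**The loss is not known.** A reader might infer that almost all the information is discarded. That holds only if crossing is rare. At 20% crossing the loss is about half, and the documents give no rate.

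**Kidney markers are not few.** Section 5 also lists creatinine clearance at other times, dialysis and several estimated or measured filtration rates. The argument is that proteinuria differs in kind, not that it is one of few.

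**The power figures are assumed, and the remedy has limits.** The median, spread, correlation and effect size all come from outside the plan. The continuous analysis would usually miss a 25% reduction too. In the settings examined it remains the more informative of the two.

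**The change is not entirely free.** A reader might suppose there is no downside. The calendar row shows no clear baseline mark, although eligibility needs a proteinuria value. Undetectable protein needs a rule before taking logs. Tests at several visits would add comparisons to a plan with no multiplicity control. These objections shape the fix below.

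**Conclusion.** The point holds as a low-cost improvement to a secondary outcome. The entry ceiling, the outcome threshold, the scheduled 24-hour protein and the absence of a continuous analysis are all in the document. The need for at least 5 v 0 events follows from 18 per arm alone.

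The rest is conditional. Most of the information is lost if crossing is uncommon (88% to 93% at 1% to 2%, 66% at 10%), and about half at 20%. For a halving of protein at an assumed median of 0.5 g, power is about 0.8 or about 0.4 for the adjusted log analysis, depending on spread and correlation, against about 0 for the count. The documents do not support calling the outcome invalid, or saying that the primary analysis is affected.

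**What to change.** In sections 4 and 5, add log 24-hour urine protein at 12 months as a proteinuria outcome. Compare the arms in a linear model with the log baseline value as covariate, and report the ratio of geometric means with a 95% CI. State a small floor for undetectable values before taking logs. Present the other visits descriptively or as supportive. Keep the number of subjects above 3 g/24 h, by arm, as a descriptive line.

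Record the proteinuria value used for eligibility as the baseline, and confirm in the calendar that it is a 24-hour value. If it is not, use the unadjusted log comparison.

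The cost is about one sentence in each section and one extra analysis, with no added subjects or follow-up collections. Because the plan has no multiplicity control, label the analysis as supportive.

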Subjects in the study are liver transplant recipients who are regularly followed with blood work and physician and nurse visits. Standard of care blood work includes a complete metabolic panel, complete blood count, and tacrolimus level. These labs are obtained twice a week the first week after discharge from the hospital, then weekly until week 12 after discharge, then every 2 weeks until month 6, then monthly until year 2.

Transplant pharmacist, [name], and nephrologist, [name], have agreed to be available to discuss adverse events, and for advice and to help manage electrolyte abnormalities.

8. Adverse Event Management

The risks to subjects on spironolactone treatment are hyperkalemia and hypertension. As stated above patients will be monitored after liver transplant regularly per liver transplant protocol that follows standard of care. Any unscheduled labs will be paid for by the study. Subjects may also develop gynecomastia which will be treated by dose reduction and if not effective discontinuation of the spironolactone.

Protocol of elevated potassium

- If subject on spironolactone 50 mg daily and potassium is greater than 5.5 mg/mL then dose reduce spironolactone to 25 mg daily, and recheck potassium in 5 days. If potassium remains greater than 5.5 meq/L then patient will be discontinued from the study.
- If subject is on spironolactone 25 mg daily and potassium is greater than 5.5 meq/L, the spironolactone will be discontinued for 7 days and the potassium level will be rechecked. If the potassium level continues to be greater than 5.5 meq/L, then the subject will be discontinued from the study at the discretion of the investigator. If the subject's potassium is within normal limits, the investigator may resume the spironolactone at the investigator's discretion.
- Sodium Bicarbonate is allowed for subjects with bicarb (CO₂) < 20 at 650 mg 2 pills twice a day for target bicarb 24 meq/L.

Treatment of hypertension

- Standard post-liver transplant protocol for hypertension will be followed with amlodipine as first line agent.
- Furosemide is allowed for hypertension or edema.
- Angiotensin converting enzyme inhibitors and angiotensin receptor blockers are contraindicated.

Most women undergoing liver transplant are post-menopausal. As part of standard of care, women are advised against pregnancy the first 3 years after liver transplant. Urine pregnancy testing will be offered to women who suspect pregnancy as part of standard of care.

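### The potassium trigger for stepping spironolactone down from 50 mg to 25 mg is printed in mg/mL instead of meq/L

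*Combined protocol and SAP*

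**What the plan says.** Section 8 (Adverse Event Management) sets out an elevated-potassium rule with one bullet for each spironolactone dose.

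- **50 mg bullet, trigger:** "If subject on spironolactone 50 mg daily and potassium is greater than 5.5 mg/mL then dose reduce spironolactone to 25 mg daily".
- **50 mg bullet, recheck after 5 days:** "If potassium remains greater than 5.5 meq/L then patient will be discontinued from the study".
- **25 mg bullet, trigger:** "If subject is on spironolactone 25 mg daily and potassium is greater than 5.5 meq/L", after which the drug is held for 7 days.
- **25 mg bullet, recheck:** "If the potassium level continues to be greater than 5.5 meq/L", after which the subject may leave the study at the investigator's discretion.

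Potassium thresholds also appear in two earlier sections. Section 3 has the screening exclusion, "Potassium greater than 5.2 meq/L on screening labs", and the escalation rule, "if potassium stays less than 5.2 meq/L after 1 month on treatment, spironolactone may be increased to 50 mg daily". Section 5 defines the hyperkalemia secondary outcome as a value above 5.5 mEq/L.

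**The concern.** The first threshold in the 50 mg bullet carries a different unit from every other potassium threshold in the document, and the number attached to it makes no sense in that unit. The bullet also disagrees with itself: its second sentence asks whether potassium *remains* above 5.5 meq/L, which presupposes that the first sentence used the same limit.

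This threshold is an operative one. Section 8 names hyperkalemia as a risk of the study drug, and subjects on 50 mg are on the highest dose the protocol allows. Their step-down has no other stated trigger: the 25 mg bullet is confined to subjects on 25 mg, and the recheck applies only after the dose has been cut. Read literally, the rule would never reduce the dose of a subject on 50 mg, whatever the potassium value. The same wrong unit could also be carried into any order set, laboratory alert or deviation check copied from the protocol.

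**Working it through.** The plan derives no figure here that could be reproduced. The check is a count of thresholds and a unit conversion.

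**Count of potassium thresholds**

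| Place | Use | Limit | Unit |
|---|---|---|---|
| Section 3, exclusion criteria | Screening exclusion | > 5.2 | meq/L |
| Section 3, end of section | Escalation to 50 mg | < 5.2 | meq/L |
| Section 5, secondary outcomes | Hyperkalemia | > 5.5 | mEq/L |
| Section 8, 50 mg bullet | Trigger for step-down | > 5.5 | **mg/mL** |
| Section 8, 50 mg bullet | Recheck | > 5.5 | meq/L |
| Section 8, 25 mg bullet | Trigger for 7-day hold | > 5.5 | meq/L |
| Section 8, 25 mg bullet | Recheck | > 5.5 | meq/L |

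One of 7 thresholds in the document, and 1 of 4 in section 8, is in mg/mL. That unit occurs nowhere else. The bicarbonate target in the same list is also in meq/L ("for target bicarb 24 meq/L").

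**Conversion**

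Input not in the documents: the atomic mass of potassium, about 39.1 g/mol, with valence 1. This is a physical constant.

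Formula: meq/L = (mg/mL × 1000) / 39.1 × 1.

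- Printed trigger: 5.5 × 1000 / 39.1 = 140.7 meq/L.
- Ratio to the hyperkalemia limit: 140.7 / 5.5 = 25.6.
- In reverse, the 5.5 meq/L limit in mg/mL: 5.5 × 39.1 / 1000 = 0.215 mg/mL.

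**Could another mass unit have been meant?** The obvious candidate is mg/dL: 5.5 × 10 / 39.1 = 1.41 meq/L. That is far below the 5.2 meq/L under which section 3 allows escalation to 50 mg, so a subject could qualify for the higher dose and for its reduction at the same potassium value. Of the three units, only meq/L agrees with the recheck, the 25 mg bullet, the escalation rule and the outcome definition.

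**The case against.** The strongest reply is that this is a self-correcting typing error. The next sentence of the bullet gives the right unit, the 25 mg bullet and the hyperkalemia outcome give the same 5.5 meq/L, and no second reading is plausible. A value near 141 meq/L is so far from anything possible that a clinician could not follow it by mistake; a wrong but believable limit would be more dangerous. Section 8 also makes a transplant pharmacist and a nephrologist available for advice on electrolyte problems. No outcome or analysis uses this trigger, because hyperkalemia is defined separately, and correctly, in section 5.

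All of this stands, and it limits the weight of the point: the 25.6-fold factor shows that the printed unit is wrong and does not measure the hazard to patients. It does not make the text right. The reader still has to infer the entry threshold of a dose-reduction rule from the sentence that follows it.

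A misreading when the PDF was converted to text cannot be strictly excluded without the source page. It is unlikely: the sentence is intact, and mg/mL is not a typical character misreading of meq/L, which was read correctly elsewhere in the same list.

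**Conclusion.** The concern holds. The step-down trigger is wrong as written: it equates to about 140.7 meq/L where 5.5 meq/L is meant, and it is the only one of seven potassium thresholds so affected. The conversion rests on the atomic mass and valence of potassium; the intended unit follows from the document itself.

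This is a minor correction to safety text. The rule concerns only subjects in the spironolactone arm (18 planned) who have been escalated to 50 mg, a number the protocol does not fix because escalation is discretionary. A missed dose reduction is unlikely in practice, since the intent is plain. Sample size, power, alpha, the primary outcome and the hyperkalemia outcome are unaffected.

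**What to change.** In section 8, 50 mg bullet, first sentence, change the unit of the 5.5 threshold from mg/mL to meq/L. The number stays as it is. The trigger then matches its own recheck, the 25 mg bullet and the section 5 outcome.

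If the rule has already been copied into order sets, laboratory alerts or monitoring checks, confirm that they use meq/L. The protocol change itself is one unit, with no cost to the analysis, the sample size or enrolment.

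### For subjects on 50 mg, the elevated-potassium rule has no upper limit: any value above 5.5 meq/L means continuing at 25 mg daily, with the next required recheck at day 5

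*Combined protocol and SAP*

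**What the plan says.** Section 3 allows treated subjects to move up from 25 mg at the investigator's discretion: "if potassium stays less than 5.2 meq/L after 1 month on treatment, spironolactone may be increased to 50 mg daily".

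Section 8 then has two rules for high potassium, one per dose.

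- On 50 mg (first bullet), a value above 5.5 means "then dose reduce spironolactone to 25 mg daily, and recheck potassium in 5 days". The exit step is "If potassium remains greater than 5.5 meq/L then patient will be discontinued from the study".
- On 25 mg (second bullet): "If subject is on spironolactone 25 mg daily and potassium is greater than 5.5 meq/L, the spironolactone will be discontinued for 7 days". If the value is still high at the recheck, "then the subject will be discontinued from the study at the discretion of the investigator".

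Three other provisions bear on the days before the recheck. The Section 6 footnote asks for "BMP weekly for 2 weeks if dose change in spironolactone". Section 7 describes standard labs that are drawn twice in the first week after discharge, "then weekly until week 12 after discharge, then every 2 weeks until month 6, then monthly until year 2". Section 7 also says that a transplant pharmacist and a nephrologist "have agreed to be available to discuss adverse events, and for advice and to help manage electrolyte abnormalities".

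**The concern.** Stepping down from 50 mg to 25 mg is sensible for a small rise, because an escalated subject had earlier tolerated 25 mg with potassium below 5.2. The difficulty is that the step has no ceiling. The same instruction applies to a value just over the threshold and to a marked one, and in both cases it is to keep giving the drug.

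The two bullets also sit oddly together. A subject already on 25 mg may not continue 25 mg at 5.6, yet a subject coming from 50 mg is given 25 mg at 7.0.

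The stake is subject safety. Section 8 names hyperkalemia as a risk of the treatment, and Section 3 admits anyone with creatinine clearance above 30 ml/min. An investigator who follows the text keeps a subject with a marked value on the drug until the recheck; one who stops the drug at once departs from the written step.

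**Working it through.** The plan states no figure to reproduce. The check sets the two rules side by side and then looks for any other provision that would require action sooner.

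**The two rules for a potassium above 5.5 meq/L (Section 8)**

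| | On 50 mg (first bullet) | On 25 mg (second bullet) |
|---|---|---|
| Upper limit on the value | none | none |
| Drug until the recheck | continues at 25 mg daily | stopped |
| Dose taken before the recheck | 5 × 25 = 125 mg (unchanged dose: 5 × 50 = 250 mg) | 0 mg |
| Required recheck | day 5 | day 7 |
| Exit if still above 5.5 | mandatory | at the investigator's discretion |

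The milligram figures describe the rule and do not measure harm. The 50 mg rule is stricter in two respects, the earlier recheck and the mandatory exit, but neither takes effect before day 5. The 25 mg rule also has no tier for an earlier recheck, but it has no gap in stopping.

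**Is there a higher threshold elsewhere?** The other potassium figures are 5.2 (entry and escalation, Section 3) and above 5.5 (outcome definition, Section 5). Neither attaches an action to a more severe value.

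**Is a test guaranteed before day 5?**

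1. The footnote test after a dose change is weekly, so the first is due at about day 7.
2. The earliest escalation is 3 weeks after transplant plus about 4 weeks on treatment, so about 7 weeks after transplant. For a subject discharged more than a week earlier, standard labs are then 7 days, 14 days or about 30 days apart. Each interval is longer than 5 days.
3. These intervals describe one schedule at a time. Standard labs run from hospital discharge, study chemistry visits from randomization, and the footnote tests from the dose change. The documents do not say that the schedules share draws. A high value on a study draw could be followed by a standard lab a few days later.

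So an early test is possible by coincidence of schedules, but none is required by the potassium value and none is guaranteed.

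**Who is exposed?** At most the 18 subjects randomized to treatment, and only those escalated. The range is 0 to 18.

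**Unit.** The opening trigger for 50 mg is printed in mg/mL. Taken literally, and assuming 39.1 mg of potassium per meq, 5.5 mg/mL = 5500 mg/L, and 5500 / 39.1 = 141 meq/L, which could never be met. The next sentence and the second bullet use meq/L, so this is a misprint, and the rule is read here in meq/L.

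**The case against.** The strongest reply is that the event is uncommon and well surrounded by safeguards. Escalation is discretionary and needs potassium below 5.2 after a month. Subjects on ACE inhibitors, angiotensin receptor blockers and other hyperkalemic drugs are excluded. A nephrologist and a pharmacist are on hand, and unscheduled labs are funded. Nothing forbids acting sooner. All of this stands, and it limits the weight of the point. It does not supply a rule for a marked value: the advisers are available, but no result triggers a call to them.

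A reader might go further in three ways that the documents do not support.

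- That no potassium will be measured before day 5. The schedules run on different clocks, so a draw may fall inside the window.
- That the center has no upper tier at all. Section 8 refers to a liver transplant protocol for standard-of-care monitoring. It is not among the documents, so the finding covers this document only.
- That subjects on 25 mg face the same problem. Their drug is stopped at any value above 5.5; what they lack is an early repeat at a high value.

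**Conclusion.** The concern holds for subjects on 50 mg. The written step keeps them on spironolactone at 25 mg daily whatever the height of the value, and nothing in this document requires an immediate stop, an earlier repeat or a call to the nephrologist. This is a stated action that is unsuitable at a marked value, so it is more than a missing detail.

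Its size is 0 to 18 subjects, with a frequency that cannot be estimated from the documents. No effect on power or on the primary result is claimed, and no harm is quantified. The conclusion rests on reading the 50 mg trigger in meq/L. It is a cheap improvement.

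**What to change.** 1. In the first bullet, limit the initial dose reduction to potassium greater than 5.5 and less than 6.0 meq/L, and print meq/L in place of mg/mL.
2. Add a rule for 50 mg: at 6.0 meq/L or higher in a non-hemolyzed specimen, stop spironolactone the same day, repeat potassium within 24 hours and contact the study nephrologist, who directs further management on the repeat value. The drug may be resumed, at no more than 25 mg daily and at the investigator's discretion, only if potassium is within normal limits after 7 days off drug. If it is still above 5.5 meq/L, the subject leaves the study.
3. State that this rule applies only to the initial value on 50 mg. After a reduction to 25 mg, a 5-day recheck above 5.5 meq/L at any level still means exit, and an interim value above 5.5 before that recheck stops the drug under the second bullet.
4. Leave the second bullet's hold and discretionary exit as they are. At 25 mg, add only the 24-hour repeat and the nephrologist contact at 6.0 meq/L or higher.

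A coverage check over 5.6 to 7.0 in steps of 0.1 gives 15 values at each dose, 30 cells in all. At 50 mg, 4 cells (5.6 to 5.9) fall under the dose reduction and 11 (6.0 to 7.0) under the new rule. At 25 mg, all 15 fall under the second bullet, 11 of them with the added repeat and contact. For a non-hemolyzed specimen, each cell has exactly one opening rule.

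The documents give no threshold above 5.5, so the 6.0 ceiling and the 24-hour interval are assumptions. A ceiling anywhere from 5.8 to 6.5 would close the gap, and the study nephrologist should confirm both figures before the amendment.

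The cost is a short amendment and about one extra potassium test per event at or above the ceiling, which Section 8 already has the study pay for. If the repeat needs a non-standard visit to the Transplant Center, Section 10 adds 25 or 50 dollars. With at most one such event per treated subject, the total is 0 to 18 × 50 = 900 dollars.

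### Read literally, the potassium rule can take only spironolactone subjects out of the study, and nothing in the plan secures their month-12 GFR or an as-randomised analysis

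*Combined protocol and SAP*

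**What the plan says.** Section 8 (Adverse Event Management, Protocol of elevated potassium) sets its rule by spironolactone dose.

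- **50 mg bullet.** After a dose reduction and a repeat test at 5 days: "If potassium remains greater than 5.5 meq/L then patient will be discontinued from the study".
- **25 mg bullet.** Drug is held for 7 days and potassium is repeated. If it is still above 5.5, "then the subject will be discontinued from the study at the discretion of the investigator"; if it is normal, the investigator may restart the drug.

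The same section words another lasting stop differently: "Subjects may also develop gynecomastia which will be treated by dose reduction and if not effective discontinuation of the spironolactone".

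Section 5 defines the primary outcome as "Change in creatinine clearance from screening to 1 year post randomization based on iothalamate GFR". Section 4 compares group means by an unpaired t test, or a Wilcoxon rank sum test if the data are not normal. It names no analysis set and no rule for missing data. Section 3 states "Patients will be monitored by SOC transplant protocol for up to 2 years". Section 7 describes what that monitoring contains: "Standard of care blood work includes a complete metabolic panel, complete blood count, and tacrolimus level", on a schedule that ends "then every 2 weeks until month 6, then monthly until year 2". Section 10 lists the iothalamate scan among the items that the study pays for.

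**The concern.** Both bullets apply only to subjects taking spironolactone. The control arm receives no treatment and no placebo, so it falls under neither bullet, and no equivalent exit is written for it. A site that follows the words as they stand could therefore withdraw treated subjects, and only treated subjects, before the month-12 scan.

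That scan is a study procedure and is not among the standard-of-care labs, so it is what a literal exit would lose. If the subjects who leave differ in GFR change from those who stay, the treated mean is computed on a selected group and the control mean is not. The estimate would favour spironolactone if those removed were doing worse and disfavour it if they were doing better. A scan that was not done cannot be recovered at analysis.

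**Working it through.** **1. What the text settles.**

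| Question | Where | Answer in the text |
|---|---|---|
| Who can be discontinued under the rule? | Section 8, both bullets | Subjects on 50 mg or 25 mg spironolactone |
| Is exit mandatory? | Section 8 | Stated flatly at 50 mg; discretionary at 25 mg |
| Is there a matching exit for controls? | Sections 3 and 8 | None written |
| Is the month-12 scan kept after exit? | Sections 3, 5, 6, 7, 10 | Not stated |
| Is analysis as randomised? | Section 4 | Not stated |
| Does other renal information survive? | Section 7 | Probably: metabolic panels monthly to year 2 |

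On the last row: entry is 3 weeks to 6 months after transplant, and the calendar allows up to 45 days from screening. Month 12 after randomisation therefore falls between about 0.7 + 12 = 12.7 and 6 + 1.5 + 12 = 19.5 months after transplant, before year 2. Creatinine-based estimates would probably exist, but they are not the primary outcome.

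**2. The SD, which the plan does not give.** Section 4 states 16 per group, a 10 ml difference, power 0.5 and p ≤ 0.05. Without an SD, the figure of 16 cannot be reproduced from stated inputs, so I solved for the SD that yields it. A two-sided t test (noncentral t) gives 13.97 ml and a two-sided normal approximation gives 14.4. One-sided versions give 16.8 (t) and 17.2 (normal). I use 13.97 below.

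Standard error of the difference at 18 per arm: 13.97 × √(2/18) = 4.66 ml.

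**3. Illustration of bias.** Assumptions: all 18 per arm are scanned, the analysis uses complete cases, there is no true effect, and k of the 18 treated subjects are removed. The link between removal and outcome is assumed: the chance of removal is weighted by exp(slope × decline in SD units). Slope 0 means no link. The ceiling row removes exactly the k subjects with the worst change. There were 200,000 simulated trials per setting.

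| Link | k = 1: bias, rejection | k = 2: bias, rejection |
|---|---|---|
| None (slope 0) | 0 ml, 5% | 0 ml, 5% |
| Slope 0.5 | 0.38 ml, 5.1% | 0.77 ml, 5.4% |
| Slope 1 | 0.73 ml, 5.5% | 1.44 ml, 6.3% |
| Slope 2 | 1.15 ml, 6.2% | 2.20 ml, 8.3% |
| Ceiling | 1.50 ml, 6.9% | 2.77 ml, 10.4% |

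The ceiling can be checked by hand. The two most extreme of 18 standard normal values have expected sizes 1.820 and 1.350.

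- k = 1: 1.820 / 17 × 13.97 = 1.50 ml.
- k = 2: (1.820 + 1.350) / 16 × 13.97 = 2.77 ml, and 2.77 / 4.66 = 0.59 standard errors.

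Bias scales with the SD. At 17.2 the ceilings are 1.820 / 17 × 17.2 = 1.84 ml and 3.170 / 16 × 17.2 = 3.41 ml. If those removed had the better change, the same figures apply with the opposite sign.

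**4. Power.** For a true 10 ml difference, power is 0.550 with 18 v 18, 0.538 with 17 v 18 and 0.524 with 16 v 18. Loss of power is not the issue.

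**The case against.** **The phrase may mean only that study drug stops for good.** In the 25 mg bullet, the alternative to being discontinued is restarting spironolactone. In the 50 mg bullet, the phrase is the only text that could stop the drug at all. Against this, the gynecomastia sentence names the drug explicitly, and in the 25 mg bullet the drug is already on hold when the phrase is used. Neither reading can be excluded. The objection stands to this extent: the plan cannot be said to remove these subjects from follow-up, only to permit that reading.

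**Silence is not a per-protocol plan.** A reader might infer that the trial intends to drop or reassign these subjects. The documents do not support that: section 3 forms two groups by randomisation and section 4 compares groups. The gap is that the analysis set is unstated; complete-case analysis is my assumption.

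**The path to exit is narrow.** The background reports acceptable hyperkalemia rates at low doses. Section 3 excludes drugs associated with high potassium and also excludes "Potassium greater than 5.2 meq/L on screening labs, one occasion in a non-hemolyzed specimen". The increase to 50 mg is discretionary, both bullets require a repeat test, and exit at 25 mg is discretionary. A reader might infer heavy loss, say a quarter of the arm; nothing in the documents supports that, so I illustrate with one or two subjects.

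**Direction is unknown.** A reader might infer that the rule favours spironolactone, on the view that high potassium marks failing kidneys. The documents show no association between exit and GFR change in either direction.

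**Not all may be scanned.** The calendar footnote allows a budget-driven subset. That is a separate matter, but it makes the standard error and the counts above less reliable.

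**Conclusion.** The point holds in a limited form. The text permits treated subjects, and only treated subjects, to leave the study before the primary outcome is measured, and nothing elsewhere prevents it. Whether that is intended needs clarification first.

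If the literal reading is followed, losing 1 of 18 gives a bias of 0 to 1.5 ml and two-sided rejection of 5 to 7%. Losing 2 of 18 gives 0 to 2.8 ml (up to about 0.6 standard errors) and 5 to 10%. The upper ends require that those removed are exactly the worst. With no association the bias is zero. These figures rest on the back-solved SD and the assumptions listed with the illustration; the documents give no SD, exit rate or association. A claim that the trial is biased, or biased in a known direction, would go beyond the evidence. I rate this a minor point and a cheap improvement.

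**What to change.** 1. **Section 8.** The clinical team should reconcile the two potassium bullets so that each states separately what happens to study drug and what happens to study follow-up. No change to thresholds or doses is proposed. The 50 mg bullet also gives its first threshold in mg/mL where the rest of the rule uses meq/L; the units should be reconciled at the same time.
2. **Follow-up.** Add, for example: *Unless consent is withdrawn, subjects who stop spironolactone have the month-12 GFR and other scheduled assessments on the same basis as controls.* If only a subset is scanned, selection must not depend on arm or on stopping drug.
3. **Section 4.** State that the primary analysis includes all randomised subjects with GFR data, in their randomised arm, whatever their treatment status.
4. **Reporting.** Give missing month-12 GFR by arm, with reasons. CKD-EPI or MDRD values from standard labs may stand in for a missing scan only in a supportive sensitivity analysis, because their agreement with iothalamate is itself one of the trial's questions.

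Cost: a rewrite of two bullets, two added sentences, and perhaps one or two extra month-12 scans. The downside is that the effect estimate will include subjects off drug and may be smaller.
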